Secondary endpoints will be summarized using descriptive statistics. Continuous endpoints with multiple post-baseline assessments will be analyzed using mixed-effect model for repeated measures methods including repeat number category, treatment group, visit, and treatment-by-visit interaction as fixed effects and baseline value as a covariate; continuous endpoints with a single post-baseline assessment will be analyzed using ANCOVA methods, with repeat number category and treatment group as fixed effects and baseline value as a covariate.

Secondary endpoints in the OLE will be summarized according to the treatment assigned at randomization. For all subjects, changes in measurements will be calculated relative to measurements obtained at baseline (ie, prior to first dose in the placebo-controlled treatment period).

Hypothesis testing on key study endpoints will be conducted using the FAS. A sequential testing procedure will be used to control for Type I Error to test the following key study endpoints: DUX4 change from baseline at Week 16 or Week 36; LMV change from baseline at Week 48, and FSHD TUG change from baseline at Week 48.

Safety data in the placebo-controlled treatment period will be analyzed using the safety analysis set and summarized by treatment group and visit (if applicable) using descriptive statistics. Safety data in the OLE will be analyzed using the open-label analysis set. Treatment-emergent AEs will be summarized by Medical Dictionary for Regulatory Activities system organ class and preferred term; separate summaries will be produced for treatment-related AEs, AESIs, SAEs, and

Fulcrum Therapeutics

Losmapimod

Protocol FIS-002-2019, Version 4.0 (COVID-19 Pandemic Emergency Amendment)

10 April 2020

discontinuations due to AEs. Laboratory tests, vital signs, findings from physical examinations, and ECGs will be summarized for changes over time during treatment using descriptive statistics.

Interim Analysis

One interim analysis (IA) will be performed after a minimum of 22 paired muscle biopsies have been collected. A group sequential method (O'Brien Fleming Spending Function) will be used to ensure an overall significance level of 0.05 (double-sided) due to multiple looks at the DUX4 primary endpoint.

Version and Date of Protocol:

Version 4.0 (COVID-19 Pandemic Emergency Amendment,
10 April 2020

Fulcrum Therapeutics

Protocol FIS-002-2019, Version 4.0 (COVID-19 Pandemic Emergency Amendment)

Losmapimod

10 April 2020

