7.6.1 Hypothesis Testing on Key Study Endpoints

Hypothesis testing on key study endpoints will be conducted using the FAS.

A sequential testing procedure will be used to control for Type I Error to test the following key study endpoints:

- DUX4 change from baseline (Week 16 or Week 36)
- LMV change from baseline (Week 48)
- FSHD TUG (Week 48)

The testing hierarchy will be provided in the SAP. Each endpoint will be tested at approximately 5% alpha in a hierarchical manner, using the final test-alpha obtained from O'Brien-Fleming Spending Function ([Section 7.6.8](#)).

Fulcrum Therapeutics

Losmapimod

Protocol FIS-002-2019, Version 4.0 (COVID-19 Pandemic Emergency Amendment)

10 April 2020

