7.6.8 Interim Analyses

One IA will be performed when a minimum of 22 paired muscle biopsies are completed. A group sequential method (O'Brien-Fleming Spending Function) will be used to ensure an

Fulcrum Therapeutics Losmapimod
 Protocol FIS-002-2019, Version 4.0 (COVID-19 Pandemic Emergency Amendment) 10 April 2020
 overall significance level of 0.05 (double-sided) due to multiple looks at the DUX4 primary endpoint, if the IA is deemed necessary by the Sponsor.

- With a sample size of approximately 22 subjects at IA, the test alpha at IA is approximately 0.001, and the final test alpha is 0.05. If the p-value from the test is <0.001 , then the study may be stopped for efficacy, or continue as planned as decided by the Sponsor. Cumulative exit probability under the alternative hypothesis is approximately 2.3% and approximately 82.3% at the IA and final analysis, respectively (SAS Version 9.4; nQuery 8 – Power and Sample Size for Group Sequential Trials, Version 8.5.1.0).
- With a sample size of 32 subjects at IA, the test alpha at IA is approximately 0.004, and the final test alpha is 0.048. If the p-value from the test is <0.004 , then the trial may be stopped for efficacy, or continue as planned as decided by Sponsor. Cumulative exit probability under the alternative hypothesis is approximately 13.9% and approximately 82.2% at the IA and final analysis, respectively (SAS Version 9.4; nQuery 8 – Power and Sample Size for Group Sequential Trials, Version 8.5.1.0).

The alphas at the time of the IA for sample sizes ranging from 22 to 32 are provided in [Table 7-1](#):

Table 7-1 Alpha at Interim Analysis and Final Analysis for Different Sample Sizes at Interim Analysis (O'Brien-Fleming Method)

Interim Analysis Sample Size	Alpha at Interim Analysis	Alpha at Final
22	0.000567	0.049755
23	0.000736	0.049685
24	0.000951	0.049596
25	0.001203	0.049493
26	0.001474	0.049384
27	0.001803	0.049253
28	0.002173	0.049107
29	0.002556	0.048959
30	0.003005	0.048787
31	0.003496	0.048602
32	0.004027	0.048405

Fulcrum Therapeutics

Protocol FIS-002-2019, Version 4.0 (COVID-19 Pandemic Emergency Amendment)

Losmapimod

10 April 2020

8 Data Quality Assurance

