8.1. Hypothesis Testing Procedure for Key Study Endpoints

A fixed sequential testing procedure will be used to control for the experiment-wise Type I Error to test the following key study endpoints as ordered below:

- DUX4 change from baseline at Week 16 or Week 36 [DUX4 Score 1. See [Section 8.2](#)]
- LMV change from baseline at Week 48 [Total LMV, composite of assessments from multiple muscles. See [Section 8.3](#)]

- FSHD TUG change from baseline at Week 48 [average completion time of FSHD TUG. See [Section 8.4.2](#)]

At each step in this sequential ordering, statistical significance for the endpoint will be claimed only if the p-value for the test is less than the final alpha obtained from the O'Brien-Fleming Spending Function ([Table 12-1](#)) and the p-values for the tests for all previous endpoints in the list are also less than the final alpha provided.

The testing hierarchy will be as follows:

- If the p-value for the test of the comparison of DUX4 change from baseline between the two treatment groups is less than the final alpha, then the comparison of the LMV change from baseline will be conducted. If the p-value from this comparison is also less than the final alpha, then the comparison of the FSHD TUG change from baseline will be conducted.
- Once a p-value is greater than or equal to the final alpha for the current endpoint being evaluated, then only the tests for the preceding endpoints will be considered significant.
- The formal statistical tests for any of the endpoints will be considered statistically nonsignificant when the test has a p-value of greater than or equal to final alpha. However, nominal p-values will still be provided for these endpoints.

8.2. Change from Baseline in DUX4 Activity in Skeletal Muscle at Week 16 or Week 36

A subset of DUX4-gene transcripts will be measured in skeletal muscle biopsies, using a validated QRT-PCR assay, to assess the treatment effect of losmapimod over placebo on aberrant DUX4 activity. A mean DUX4 score (DUX4 Score 1) will be derived for each patient, at each time point based on normalized gene expression values for the panel of pre-selected genes. DUX4 Score 1 is a mean of normalized (delta-CT) for the pre-selected panel of 6 genes, by subject, for each timepoint.

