Initially, no interim analysis for efficacy was planned. However, based on protocol version 4.0 (COVID-19 Pandemic Emergency Amendment) dated 10Apr2020, an interim analysis was included to provide timely data to inform the further development of losmapimod for the treatment of FSHD.

One IA will be performed when a minimum of 22 paired muscle biopsies are completed. A group sequential method (O'Brien-Fleming Spending Function) will be used to ensure an overall significance level of 0.05 (double-sided) due to multiple looks at the DUX4 primary endpoint, if the IA is deemed necessary by the Sponsor.

- With a sample size of approximately 22 subjects at IA, the test alpha at IA is approximately 0.001, and the final test alpha is 0.05. If the p-value from the test is <0.001 , then the study may be stopped for efficacy, or continue as planned as decided by the Sponsor. Cumulative exit probability under the alternative hypothesis is approximately 2.3% and approximately 82.3% at the IA and final analysis, respectively (SAS Version 9.4; nQuery 8 – Power and Sample Size for Group Sequential Trials, Version 8.5.1.0).
- With a sample size of 32 subjects at IA, the test alpha at IA is approximately 0.004, and the final test alpha is 0.048. If the p-value from the test is <0.004 , then the trial may be stopped for efficacy, or continue as planned as decided by Sponsor. Cumulative exit probability under the alternative hypothesis is approximately 13.9% and approximately 82.2% at the IA and final analysis, respectively (SAS Version 9.4; nQuery 8 – Power and Sample Size for Group Sequential Trials, Version 8.5.1.0).

The alpha at the time of the IA for sample size ranging from 22 to 32 are provided in [Table 12-1](#)

Table 12-1 Alpha at Interim Analysis and Final Analysis for Different Sample Sizes at Interim Analysis (O'Brien Fleming Method)

Interim Analysis Sample Size	Alpha at Interim Analysis	Alpha at Final
22	0.000567	0.049755
23	0.000736	0.049685
24	0.000951	0.049596
25	0.001203	0.049493
26	0.001474	0.049384
27	0.001803	0.049253
28	0.002173	0.049107
29	0.002556	0.048959
30	0.003005	0.048787
31	0.003496	0.048602
32	0.004027	0.048405

The DUX4, PK, demographics, disposition data and sub-group analysis on the DUX4 endpoint ([Section 4.6, #1 to #5](#) and [#11](#)) will be presented to the Sponsor as group-level summaries of the unblinded data with associated p-values. The respective tables are indicated in the List of Planned Summary Tables.

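### The interim stopping text at about 22 pairs (p<0.001) is looser than the tabulated boundary at 22 to 24 pairs, and the named method and the 32-pair exit probabilities do not belong to the table

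*SAP*

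**What the plan says.** SAP Section 12 and Protocol 7.6.8 carry the same interim text. One look at the DUX4 primary endpoint takes place once at least 22 paired biopsies are available; no maximum is given.

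- **Method.** An O'Brien-Fleming "Spending Function) will be used to ensure an overall significance level of 0.05 (double-sided) due to multiple looks at the DUX4 primary endpoint". The Protocol synopsis, Protocol 7.6.1 and SAP 8.1 use the same label. The table title instead calls it the O'Brien-Fleming method: "Alpha at Interim Analysis and Final Analysis for Different Sample Sizes at Interim Analysis".
- **About 22 subjects.** "the test alpha at IA is approximately 0.001, and the final test alpha is 0.05". The study may be stopped for efficacy "If the p-value from the test is <0.001", or continue, as the sponsor decides. Exit probabilities: 2.3% at the interim, 82.3% cumulative.
- **32 subjects.** Interim alpha about 0.004, final 0.048, stopping at p<0.004. "Cumulative exit probability under the alternative hypothesis is approximately 13.9% and approximately 82.2% at the IA and final analysis, respectively".
- **Table 12-1 / 7-1.** Interim / final alpha runs from 0.000567 / 0.049755 at 22 pairs to 0.004027 / 0.048405 at 32.

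SAP 4.1 sends statistical tests to the levels in Table 12-1 unless otherwise specified. SAP 8.1 says significance "will be claimed only if the p-value for the test is less than the final alpha obtained from the" O'Brien-Fleming calculation in that table, and SAP 8.2 also takes the final alpha from there.

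**The concern.** The stopping sentence looks like the 22-pair table entry rounded up to three decimals. An interim p of 0.0008 at 22 pairs would cross the boundary under the text and miss it under the table. SAP 4.1 leans towards the table, but its exception for anything otherwise specified leaves an explicit p<0.001 rule standing. The word approximately qualifies the test alpha, not the stopping sentence.

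This is the only efficacy look at the primary endpoint. The sponsor sees group-level unblinded results with p-values and decides whether to stop. Whether the boundary was crossed should not depend on which line is read.

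The method label matters as well. The table stops at 32 pairs and the look has no upper limit, so a statistician with more pairs would have to compute the boundary from the named method.

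**Working it through.** **Inputs.** Overall two-sided alpha 0.05 and 22 to 32 pairs (SAP 12); effect size 0.70 and 68 evaluable subjects, 34 per group (SAP 4.7, Protocol 7.3). Information fraction t = n/68. Under the null the two test statistics are bivariate normal with correlation √t.

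**1. Reproduce the table.** The classical two-look O'Brien-Fleming boundary is c1 = C/√t at the interim and c2 = C at the end, with C solved so that P(reject at either look) = 0.05. Each nominal alpha is 2(1 − Φ(c)).

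- 22 pairs: t = 22/68 = 0.324 (three decimals), C = 1.96206, c1 = 1.96206/√0.324 = 3.447. Alphas 0.000567 and 0.049755.
- 32 pairs: t = 0.471, C = 1.97380, c1 = 2.876. Alphas 0.004027 and 0.048405.

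All 11 rows match to six decimals in both columns. The match needs t rounded to three decimals; unrounded t gives 0.000562 at 22 and 0.004012 at 32. It also fixes N: at 22 pairs, N = 67 gives 0.000612 and N = 69 gives 0.000514.

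**2. Test the named method**, with the same rounded t.

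| Interim alpha | 22 pairs | 32 pairs |
|---|---|---|
| Table | 0.000567 | 0.004027 |
| Classical boundary | 0.000567 | 0.004027 |
| Spending per side, 4(1 − Φ(2.2414/√t)) | 0.000165 | 0.002182 |
| Spending on two-sided total, 2(1 − Φ(1.96/√t)) | 0.000575 | 0.004292 |

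Neither spending form reproduces the table.

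**3. Text against table.** Overall type I error uses an interim cut-off of 0.001 with the table's final alpha. The last column is the chance, at effect size 0.70, that the interim p falls between the two thresholds (normal theory).

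| Pairs | Table | 0.001 / table | Overall alpha | Chance of falling between |
|---|---|---|---|---|
| 22 | 0.000567 | 1.76 | 0.0502 | 1.4% |
| 23 | 0.000736 | 1.36 | 0.0501 | 0.9% |
| 24 | 0.000951 | 1.05 | 0.0500 | 0.2% |
| 25 | 0.001203 | 0.83 | 0.0499 | none (table is looser) |

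At 32 pairs the text's 0.004 lies just below 0.004027 and does no harm.

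**4. Exit probabilities.** Normal theory uses drift 0.70√(n/4): 1.642 at 22, 1.980 at 32, and 0.70√17 = 2.886 at 68. The t column uses noncentral t with n − 2 degrees of freedom at the table's interim boundary.

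| Pairs | Stated | Table boundary, normal | Table boundary, interim by t | Per-side spending, normal |
|---|---|---|---|---|
| 22 | 2.3% / 82.3% | 3.6% / 82.2% | 2.1% | 1.7% / 82.3% |
| 32 | 13.9% / 82.2% | 18.5% / 82.1% | 15.2% | 13.9% / 82.2% |

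At 32 pairs both stated figures match per-side spending. At 22 pairs the stated 2.3% matches no column; per-side spending reaches 2.3% at 23 pairs.

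**The case against.** **The practical effect is negligible.** Overall alpha moves by about 0.0002 at worst, the exact values are printed directly below the text, SAP 4.1 points to the table, and stopping is optional. All of this stands. It limits the size of the point but does not remove the second threshold.

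**The stated exit probabilities may be sound.** A reader might infer from the normal-theory column that the plan understates the chance of early crossing. The documents do not support that. The planned test is an ANCOVA, so a t reference is at least as apt with 22 to 32 subjects. On that basis the table gives 2.1% at 22 pairs, slightly below the stated 2.3%, and 15.2% at 32, which is 1.3 points above the stated 13.9%. What survives is narrower. The 32-pair figures match a rule other than the tabulated one, and the stated cumulative values follow normal theory: a single test at 34 per group has 82.3% power by normal theory and 81.2% by t. The software output cited in SAP 12 is not available to settle the 22-pair figure.

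**Relabelling alone would leave a gap.** The table ends at 32 pairs and assumes 68 final pairs, while 80 subjects were enrolled. This is right, so the fix has to supply a formula as well as a name.

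**The four-decimal rule in SAP 4.1 concerns reporting, not decisions.** Also right. But a printed 0.0006 covers 0.00055 to 0.00065, on both sides of 0.000567, so one line saying that the unrounded p-value is compared is worth having.

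**Conclusion.** The inconsistency is real and minor. Text and table give different interim thresholds, and the text is the looser one at 22 to 24 pairs. The table is the classical O'Brien-Fleming boundary for 68 final pairs, so the spending-function label is wrong for it. The exit probabilities at 32 pairs belong to per-side spending; those at 22 pairs cannot be traced.

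A reader might infer a material loss of error control, or a doubtful final alpha. Neither follows. With the table's final alpha, overall error is at most about 0.0502. It would be 0.0505 at 22 pairs if the rounded final 0.05 in the text were used too, but SAP 8.1 and 8.2 take the final alpha from the table.

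The error rates rest on bivariate normal theory with 68 final pairs, and the exit probabilities also on an effect size of 0.70. The identification of the table rests on exact reproduction of all its rows.

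**What to change.** In both documents:

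1. State that the unrounded Table 12-1 / 7-1 value for the observed number of pairs is the only interim efficacy threshold, in place of p<0.001 and p<0.004, and that the unrounded p-value is compared with it.
2. Name the method as the classical O'Brien-Fleming boundary at information fraction n/68, in the Protocol synopsis, Protocol 7.6.1 and 7.6.8, and SAP 8.1 and 12. Say that the same formula applies if the interim has more than 32 pairs or the planned final N differs from 68.
3. Recompute the exit probabilities from that boundary and state the basis: at the interim, about 3.6% (normal) or 2.1% (t) at 22 pairs, and 18.5% or 15.2% at 32.

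The table's final alphas stay as they are. The cost is wording in two documents and one re-run. The downside is a slightly stricter threshold at 22 to 24 pairs: at 22 pairs the chance of crossing under the planned effect falls from 5.0% to 3.6% by normal theory, or from 3.2% to 2.1% by t.

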15.1. The Steps from Raw QPCR Ct to Statistical Analysis

1. Raw Cts from qPCR are determined for DUX4 regulated genes using a validated assay (Fluidigm), described in [Appendix 15.2](#).
2. The raw Cts from the genes are normalized to reference (housekeeping) genes using the process described in [Appendix 15.3](#). The document also describes the method for selecting the reference genes.
3. A mean DUX4 score is created for each subject using the normalized data, at baseline and post-baseline, using the derivation described in [Appendix 15.4](#).
 - a. Six DUX4-regulated gene transcripts were selected, a priori, to be in a mean DUX4 score. The process of selection of these 6 genes is detailed in [Appendix 15.5](#).
4. An ANCOVA regression model is then used to test the hypothesis for change in the composite score between treatment arms.

15.4. Derivation of DUX4 Score from Delta CT

Select only rows pertaining to the following 6 gene transcripts: CCNA1; KHDC1L; MBD3L2; PRAMEF6; SLC34A2; ZSCAN4

DUX4 Score 1: Mean

Take the mean of delta-CT values across all 6 transcripts, by subject, by timepoint

DUX4 Score 2: Standardized Z-Score Composite

Step 1 (Pre-Treatment data only): (By gene transcript)

- I. Calculate Mean (measure of average) of delta CT
- II. Calculate standard deviation (measure of variability) of delta CT

Step 2 (Pre-treatment and post-treatment: By gene transcript; by subject)

- I. Use variability obtained in Step 1 to calculate standardized score per gene transcript, per patient:

$$\begin{aligned} \text{Standardized Score} \\ = (\text{Normalized Delta Ct Value} - \text{Mean}) \div \text{Standard Deviation} \end{aligned}$$

- a. **Rationale:** Standardize all gene measures to the same scale; reduce the impact of highly variable genes in the final composite measure
- II. Calculate mean of standardized scores for each patient, across all genes, by visit.
 - a. Each patient's final score is the mean standardized score across multiple transcripts.
 - b. This "composite score" is then used in the analysis for change from baseline.

DUX4 Score 3: Median

Take the median of delta-CT values across all 6 transcripts, by subject, by timepoint

15.5. Selection of 6 gene transcripts

[figure not shown]
DocuSign Envelope ID: 935905FF-DD31-42F6-A9FB-5722E6DCACAE

SAP Addenda
Fulcrum Compound Number losmapimod
STUDY NUMBER(S): FIS-001-2019
REPORT DATE: April 22, 2020
SAP-FIS-001-2019 addenda

1.0 BACKGROUND

FSHD is caused by aberrant expression of DUX4, a transcription factor encoded in the D4Z4 macrosatellite repeat array on chromosome 4q35. DUX4 is a master regulator of embryogenesis and it is normally expressed for a very short period of time in the early embryo to then be permanently repressed in later stages during development. Expression of DUX4 and genes activated by this transcription factor in the skeletal muscle of FSHD patients lead to muscle cell death that over time results in significant, progressive disability.

Figure 1: Schematic describing the loss in gene repression caused by contraction of D4Z4 repeats that leads to DUX4 expression.

The evidence that aberrant expression of the DUX4 transcriptional program is the cause of FSHD is the following:

- In people with a permissive DUX4 allele on chromosome 4q35, two very different genetic mutations (a deletion in FSHD1 and a loss of function mutation in FSHD2) converge on causing hypomethylation of the D4Z4 macrosatellite repeat array proximal to the DUX4 gene that enables it to be abnormally turned on
- The aberrant expression of the DUX4 transcriptional program clearly differentiates muscle in FSHD that, based on MRI, is normal (DUX4 activity absent) or affected (DUX4 activity present)

CONFIDENTIAL

2

15.6. Derivation of MRI Composite Score

Input to the Statistical Plan for FSHD analysis

Muscle categorization

Each muscle is categorized into one of three categories¹:

- A. 'Normal' muscles are normal appearing (low MFI and MFF, muscle likely unaffected by disease)
- B. 'Affected' muscles have a likely disease involvement (intermediate MFI and MFF)
- C. 'End-stage' corresponds to that more than 50% of the muscle tissue has been replaced by fat, and most of the functional capacity is likely lost

Muscle category	MFF criteria	MFI criteria	
A. Normal	MFF < 50%	AND	MFI < 10%
B. Affected	MFF < 50%	AND	MFI ≥ 10%
C. End-stage	MFF ≥ 50%	-	-

Quality control of measurements

Trained anatomical imaging experts evaluate the signal quality in each muscle. If a muscle is not analyzable, that muscle is marked as not analyzable and no measurements will be extracted from it. For cross-sectional analysis minor quality issues are accepted, but not for longitudinal analysis. Hence, as seen below, we'll use different statistical inclusion parameters depending on if we are doing a cross-sectional or longitudinal analysis.

Statistical inclusion parameters

The muscle categorization and quality control results are summarized in 3 statistical inclusion parameters which will be provided for each muscle:

- Statistical Inclusion Category: Can take the values **A**, **B** or **C**, which correspond to 'Normal', 'Affected' and 'End-stage'. Abbreviated SI_{cat} in equations.
- Statistical Inclusion Cross-sectional: Can take the values **0** or **1** (0 if there are major signal quality issues indicating unreliable measurement, 1 otherwise). Abbreviated SI_{cross} in equations.
- Statistical Inclusion Longitudinal: Can take the values **0** or **1** (0 if there are any signal quality issues, including minor, 1 otherwise). Abbreviated SI_{long} in equations.

Note: In general, if a SI parameter is 'Unable to Assess', 'NA' or '0', that muscle should be excluded from the corresponding data analysis. As for other muscle measurements, the SI parameters will have a corresponding 'Quality Issues' column – these columns may be ignored.

Whole-body combined measurements

Cross-sectional analysis

41

MRI-based measurements from multiple muscles is combined to obtain global measurements of disease affection for correlation to disease severity or functional test scores in cross-sectional data:

